Official Title: Pilot study evaluating the utility of OncoCEETM (Cell Enrichment and Extraction) technology, a novel immunocytochemical microfluidic device, in the diagnosis of leptomeningeal metastasis (LM) from solid tumors through identification of circulating tumor cells (CTCs) in cerebrospinal fluid (CSF)

Unique Protocol ID: AAAQ4761

Registration Identifier: NCT02948751

Document Date: July 17, 2018

Columbia University Medical Center
Herbert Irving Comprehensive Cancer Center

TITLE Pilot study evaluating the utility of OncoCEE™ (Cell Enrichment and Extraction) technology, a novel immunocytochemical microfluidic device, in the diagnosis of leptomeningeal metastasis (LM) from solid tumors through identification of circulating tumor cells (CTCs) in cerebrospinal fluid (CSF).

PRINCIPAL INVESTIGATOR

[name], MS
Assistant Professor of Medicine
Columbia University Medical Center
[contact]
E-mail: [contact]

[name]
Assistant Professor of Neurology
Columbia University Medical Center
[contact]
E-mail: [contact]

FUNDING AGENCY

NIH R03 (1 R03 CA208547-01)
Biocept, Inc

Protocol Synopsis

Title	Pilot study evaluating the utility of OncoCEE™ (Cell Enrichment and Extraction) technology, a novel immunocytochemical microfluidic device, in the diagnosis of leptomeningeal metastasis (LM) from solid tumors through identification of circulating tumor cells (CTCs) in cerebrospinal fluid (CSF).
Short Title	Microfluidic device to diagnose leptomeningeal metastasis in solid tumors
Study Duration	Approximately 24 months
Study Center(s)	Single center
Primary Objectives	Determine whether the microfluidic device will demonstrate a greater sensitivity for the detection of leptomeningeal metastasis (LM) in solid tumors as compared to standard cytopathologic analysis
Number of Subjects	46
Diagnosis and Main Inclusion Criteria	Patients with solid tumors who are undergoing lumbar puncture for suspicion of leptomeningeal metastasis
Statistical Methodology	We anticipate that using OncoCEE will result in a 25% improvement in the sensitivity to detect leptomeningeal metastasis vs. standard cytopathologic analysis on the first lumbar puncture (75% vs. 50%). We will have 80% power to detect this difference on the first lumbar puncture in 36 evaluable patients with unequivocal or suspicious findings (two-sided alpha, 0.05). In addition, we will accrue 10 patients with positive CSF fluid to compare OncoCEE in patients with definitive LM.

**Columbia University Medical Center

1. INTRODUCTION

This document is a protocol for a human research study. This study is to be conducted according to US and international standards of Good Clinical Practice (FDA Title 21 part 312 and International Conference on Harmonization guidelines), applicable government regulations and Columbia University Medical Center institutional research policies and procedures.

2. STUDY OBJECTIVES

2.1 Primary Objective

Determine whether OncoCEE™ Cell Enrichment and Extraction technology, a novel immunocytochemical microfluidic device, will demonstrate improved sensitivity in the diagnosis of leptomeningeal metastasis (LM) from solid tumors through identification of circulating tumor cells (CTCs) in the cerebrospinal fluid (CSF) as compared to standard cytopathologic analysis.

2.2 Secondary Objective(s)

- Assess the feasibility of determining estrogen, progesterone and HER2 receptor status for breast cancer patients on the CSF CTCs collected by OncoCEE™ technology
- Assess concordance between the receptor status of the primary and/or metastatic breast tumor, and that of the leptomeningeal cells collected by OncoCEE™ technology
- Explore characteristics of the CTCs and cell free DNA collected from CSF and compare them to CTCs and cell free DNA collected simultaneously from peripheral blood. Examples include BRAF mutations in melanoma and EGFR mutations in non-small cell lung cancer.
- Explore the performance of OncoCEE™ technology and standard cytopathology in diagnosing LM within 2 subgroups: patients with unequivocal MRI findings of the CNS and those with suspicious MRI findings of the CNS
- Explore the yield of checking for CSF CTCs and cell free DNA from CSF in individuals who have had an initial negative LP by standard cytopathologic and CTC analysis, for whom an additional LP is otherwise clinically warranted

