4. STUDY DESIGN

4.1 General Design

This study will prospectively enroll 36 evaluable subjects with solid tumors who are undergoing workup for clinical suspicion of leptomeningeal metastasis (LM) for unequivocal or suspicious findings by imaging or clinical determination. Neuroimaging consisting of MRI of the brain or total spine (or both, as clinically indicated) will be obtained in all patients. Patients will also undergo a lumbar puncture and standard CSF evaluation, which may consist of intracranial pressure measurement, CSF protein, glucose, white and red cell analysis, infectious cultures, as well as conventional cytopathologic analysis (cytocentrifuge). An additional CSF sample will be obtained for evaluation of CSF CTCs by OncoCEE™ technology and cell-free DNA (recommended amount: 1 tube, 10 mL) at the time of lumbar puncture.

We will define LM as previously described [14]. Patients will be considered to have a definitive diagnosis of LM if they have a positive CSF cytology.. We will accrue 10 patients with positive cytology. Unequivocal MRI findings will be defined as leptomeningeal enhancement with subarachnoid nodules, enhancement in basal cisterns, or enhancement/clumping of nerve roots. Findings such as multiple superficial brain metastases, intraventricular masses, dural enhancement associated with epidural metastasis, or new hydrocephalus will be considered suspicious but nondiagnostic. Patients with unequivocal or suspicious findings on imaging or clinical findings (without known CSF positivity) will be eligible for this study (n=36).

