5.4 Subject Recruitment

Patients with solid tumors who are undergoing lumbar puncture for suspicion of leptomeningeal metastasis will be screened by the treating clinical staff for eligibility. Upon providing informed consent, we will be notified so that preparations can be made for study inclusion. Clinical research coordinators

**Columbia University Medical Center
Herbert Irving Comprehensive Cancer Center**

will be allowed to consent study patients.

At the time of obtaining consent, consent will be requested for blood tests to check peripheral blood CTC's and circulating DNA (2 tubes, 10 cc mL each), as well as consent for additional CSF from subsequent taps, to be performed if clinically indicated, usually in the setting of an initially negative tap.

Patient visits, lumbar punctures, CSF collection, clinical evaluation and data reporting will take place at Columbia University Medical Center. CSF collection from 46 eligible breast cancer subjects is estimated to take approximately 24 months.

Study Calendar

	Pre-Enrollment	Lumbar Puncture (LP) #1	LP #2 (if clinically indicated, i.e. previously negative tap)	LP #3 (if clinically indicated, i.e. previously negative tap)	Clinical Follow-up (2 and 6 month after LP #1)
Informed Consent	X				
Inclusion/Exclusion	X				
Standard Cytologic Assessment (CSF)		X	X	X	
OncоЗEE (CSF)		X	X	X	
OncоЗEE (peripheral blood)		X	X	X	
Assess Report of Metastatic Tumor (or Primary, if not available) – ER/PR/HER2, if breast cancer, as well as mutational profile for solid tumors		X			
Patient Status (unequivocal vs. suspicious for LM)	X				X ^a

^a Patients will be followed at two additional time periods after LP #1: 2 (+/- 1 month) and 6 months (+/- 1 month) after LP #1. The goal of this is to determine LM status: unequivocal vs. suspicious and whether this changes over time (i.e. suspicious to unequivocal). If the patient is not able to come in, communication with the patient over the phone is acceptable (but not ideal).

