8. STATISTICAL CONSIDERATIONS

8.1 Study Design/Endpoints

CSF cytopathologic analysis is the gold standard in providing diagnostic confirmation of LM, but is associated with a relatively low sensitivity (approximately 50% on the first lumbar puncture) and is highly examiner-dependent. Repeat, multi-site and high volume lumbar punctures are often required, which may increase sensitivity up to 90% [7], but are associated with complications, treatment delays, and patient discomfort. We anticipate that using OncoCEE will result in a 25% improvement in the sensitivity to detect leptomeningeal metastasis vs. standard cytopathologic analysis on the first lumbar puncture (75% vs. 50%). We will have 80% power to detect this difference on the first lumbar puncture in 36 evaluable patients (two-sided alpha, 0.05) in patients with unequivocal or suspicious findings radiographically or clinically for LM. No false positives are assumed with this method, as seen with pilot data in peripheral blood (A.3). With this population, we anticipate that the prevalence of LM, defined as positive CSF cytopathologic analysis on lumbar puncture at any time point, will be approximately 90% (i.e. 32 out of 36 patients). In addition, we will accrue evaluable 10 patients with positive CSF fluid to compare OncoCEE in patients with definitive LM. Thus, the total sample size for the study will be 46 patients.

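### LM is confirmed by cytology at any tap but re-tapping is discretionary, so sensitivity in the MRI subgroups is biased and the subgroups may appear to differ when the tests do not

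*Combined protocol and SAP*

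**What the plan says.** Protocol section 2.2 lists, as an exploratory secondary objective, the performance of both tests in diagnosing LM within two subgroups: "patients with unequivocal MRI findings of the CNS and those with suspicious MRI findings of the CNS". It does not define performance, give subgroup sizes, or name the reference standard for this objective.

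The statistics section supplies the only operational reference: "LM, defined as positive CSF cytopathologic analysis on lumbar puncture at any time point" (8.1). Section 4.1 likewise ties a definitive diagnosis to positive CSF cytology. It also points to a published LM definition whose content is not in the documents. It describes the second MRI category as findings that "will be considered suspicious but nondiagnostic", and does not say whether unequivocal findings alone establish LM.

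Further taps are discretionary. The study calendar in 5.4 heads the second-tap column "LP #2 (if clinically indicated, i.e. previously negative tap", the third-tap column carries the same condition, and 2.2 likewise refers to additional taps that are clinically warranted. MRI status is recorded before enrolment. The visits at 2 and 6 months track whether status moves from suspicious to unequivocal, but no text makes that status part of the LM reference. No rule covers patients who are tapped once or never confirmed.

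**The concern.** First-tap cytology has two roles here. It is one of the tests being compared, and a positive result is enough to place the patient in the LM denominator. A patient it misses can enter only through a later positive tap, and nobody has to have one. Cytology's misses therefore drop out of the denominator selectively, and with them the cases in which OncoCEE could show an advantage.

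How far this goes depends on the share of first-tap negatives who are re-tapped. Because the treating physician knows the MRI category when deciding on another tap, that share could differ between the subgroups. Section 6.1 keeps the OncoCEE result from the treating physician, so OncoCEE cannot drive re-tapping, but nothing equivalent applies to MRI. A difference between subgroups in sensitivity, or in the OncoCEE gain, could then reflect who was re-tapped and not how the tests perform.

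**Working it through.** **Inputs from section 8.1**
- First-tap sensitivity: cytology s = 0.50, OncoCEE 0.75.
- Cytology sensitivity with repeat taps: up to 0.90. Taking 0.90, the yield of re-tapping among LM patients missed at the first tap is c = (0.90 − 0.50)/(1 − 0.50) = 0.80.

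**Inputs the documents do not give (assumed)**
- r: share of first-tap cytology-negative LM patients who are re-tapped, varied from 0 to 1.
- a and b: probability that OncoCEE is positive given first-tap cytology positive or negative, with 0.5a + 0.5b = 0.75. Two cases: full overlap (a = 1, b = 0.5) and independence (a = b = 0.75).

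**The plan's own figure.** Section 8.1 expects about 90% cytology-confirmed LM, 32 of 36; 32/36 = 88.9%, which agrees. Among true LM patients the confirmed share is s + (1 − s)rc = 0.5 + 0.4r, which reaches 0.90 only at r = 1. So 90% of enrolled patients confirmed needs essentially every patient to have LM and every first-tap negative to be re-tapped. If all 36 had LM, r = 0.5 would confirm 0.70 × 36 = 25.2 and r = 0 would confirm 18. The 80% power statement concerns the primary comparison and does not enter here.

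**Formulas**
- Confirmed share: C = s + (1 − s)rc
- Apparent cytology sensitivity: s/C
- Apparent OncoCEE sensitivity: [sa + (1 − s)rcb]/C

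**Worked values**
- r = 0.25: C = 0.5 + 0.1 = 0.60; cytology 0.50/0.60 = 83.3%. OncoCEE with full overlap (0.5 + 0.1 × 0.5)/0.60 = 91.7%, gain +8.3 points. OncoCEE under independence 75%, gain −8.3 points.
- r = 0.90: C = 0.5 + 0.36 = 0.86; cytology 0.50/0.86 = 58.1%. OncoCEE with full overlap (0.5 + 0.36 × 0.5)/0.86 = 79.1%, gain +20.9 points. OncoCEE under independence 75%, gain +16.9 points.

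| r | Confirmed share | Cytology | Gain, full overlap | Gain, independence |
|---|---|---|---|---|
| 0 | 50% | 100% | 0 | −25.0 |
| 0.25 | 60% | 83.3% | +8.3 | −8.3 |
| 0.30 | 62% | 80.6% | +9.7 | −5.6 |
| 0.50 | 70% | 71.4% | +14.3 | +3.6 |
| 0.90 | 86% | 58.1% | +20.9 | +16.9 |
| 1 | 90% | 55.6% | +22.2 | +19.4 |

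The true gain is 25 points in every row. With r = 0.25 in one subgroup and 0.90 in the other, the artificial gap in gain is 20.9 − 8.3 = 12.6 points under full overlap and 16.9 + 8.3 = 25.2 points under independence. With the same r in both, the gap is zero.

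**Precision.** With an assumed 16 true LM patients per subgroup, 0.60 × 16 = 9.6 and 0.86 × 16 = 13.76 are confirmed. Rounded, cytology is positive in 8 of 10 and 8 of 14, for which Fisher's exact test gives p ≈ 0.39.

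**Check on the remedy.** First-tap positivity over all evaluable patients does not depend on r, but with no false positives the difference equals LM prevalence times the gain. At illustrative prevalences of 100% and 60%, the same tests give 75 − 50 = 25 points and 45 − 30 = 15 points. The ratio is 75/50 = 1.5 and 45/30 = 1.5, so it does not move with prevalence.

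**The case against.** The strongest reply is that unequal re-tapping is not documented. No section gives a re-tap rate by MRI category, and the calendar's trigger, a previously negative tap, applies to both groups. A reader might infer that unequivocal-MRI patients will be re-tapped less, since their diagnosis already looks secure and the background section mentions the burden of repeat taps. The documents do not support that as fact. The same section says repeat taps are often required and that cytology provides confirmation. The direction could also reverse: a negative tap beside strong MRI findings may prompt another, and one beside weaker findings may lower suspicion. This objection stands, and limits the contrast between subgroups to a possibility.

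Other replies stand in part:
- The expected 32 of 36 implies near-universal re-tapping, which would largely remove the contrast. The 25% and 90% scenario confirms only 23.4 of 32 true LM patients. However, 32 of 36 is an expectation, and no procedure in the plan secures it.
- Cytology may not be the sole reference, because 4.1 cites an outside definition. If that definition counted unequivocal MRI as diagnostic, the subgroups would have unlike reference standards, which would not help the comparison.
- OncoCEE's own sensitivity need not shift: under independence it stays at 75%. The gain still shifts, and by more than under full overlap.
- The objective is exploratory and the subgroups are small, so the artefact would be hard to separate from chance. That lowers the stakes but does not make the estimate interpretable.

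**Conclusion.** The point holds as a limit on interpretation. With LM defined by any-time cytology and re-tapping discretionary, apparent cytology sensitivity is inflated and the OncoCEE gain understated in each MRI subgroup. At the plan's sensitivities the apparent gain is below the true 25 points at every re-tap rate tabulated, in both overlap cases.

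An artificial difference between the subgroups arises only if re-tap rates differ by MRI category. At assumed rates of 25% and 90% it would be about 13 points in the gain under full overlap and 25 under independence. These sizes rest on the assumed re-tap rates, the overlap assumption and a cumulative cytology sensitivity of 90%.

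A reader might go further and conclude that the subgroups will differ, or that the trial will report OncoCEE as adding little when MRI is unequivocal. Neither follows: no differential re-tapping is documented, its direction is uncertain, equal rates give no contrast, and the plan does not commit to contrasting the subgroups. This is a worthwhile correction to an exploratory analysis and does not bear on the validity of the trial as a whole.

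**What to change.** Specify the analysis for the MRI-subgroup objective in section 8:

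1. Within each subgroup, report the first-tap positivity of each test over all evaluable patients, with the paired difference and an exact confidence interval.
2. For any comparison between subgroups, use the ratio of the two positivity rates. Under the no-false-positive assumption in 8.1 this estimates relative sensitivity and, unlike the difference, does not scale with LM prevalence.
3. Report by subgroup the share of first-tap cytology-negatives who were re-tapped and the share of patients confirmed by cytology.
4. State that differences between subgroups in sensitivity against any-time cytology will not be interpreted as differences in test performance.
5. If all unequivocal-MRI patients are treated as having LM, present that only as a labelled sensitivity analysis, because it gives the two subgroups unlike reference standards and 4.1 does not say that such findings confirm LM.

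The cost is analysis wording only: the first-tap results and any later taps are already in the calendar, and no added procedure is needed. The downsides are that the ratio depends on the no-false-positive assumption, which 8.1 supports with peripheral blood data, and that estimates will be imprecise in small subgroups.

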3. BACKGROUND

Leptomeningeal Disease

Leptomeningeal metastasis (LM) is a condition in which cancer cells seed the meninges and may go on to invade the brain parenchyma, spinal cord, cranial nerves or peripheral nerves [1]. It is a devastating complication in solid tumors , and is often considered in the differential diagnosis when patients with

**Columbia University Medical Center
Herbert Irving Comprehensive Cancer Center**

cancer present with new neurologic symptoms [2]. The incidence varies by tumor subtypes. For instance, it was previously thought to be a rare occurrence in breast cancer, but autopsy series have shown the true overall incidence to be up to 8% [3]. In fact, while the incidence of meningeal metastasis from other malignancies has decreased, the opposite is true of breast cancer, in which clinical evidence suggests an increasing incidence.

Diagnosing Leptomeningeal Metastasis

Diagnosing LM can be difficult, particularly at early stages. The diagnosis has traditionally been based on CSF cytologic analysis and more recently has incorporated MRI findings upfront [4]. Brain and spine MRIs have been increasingly preferred for the initial evaluation of LM because of their noninvasive nature and convenience to patients. However, MRI findings can be equivocal, and unequivocal findings may only appear in late-stage disease. CSF cytopathologic analysis provides diagnostic confirmation of LM, but is associated with a relatively low sensitivity (approximately 50% on the first lumbar puncture) and is highly examiner-dependent [5, 6]. Repeat, multi-site and high volume lumbar punctures are often required [7], which may increase sensitivity up to 90%, but are associated with complications, treatment delays, and patient discomfort.

Peripheral Blood CTC's

Analysis of peripheral blood CTCs has been explored as a prognostic marker of disease and response to anticancer treatments in breast cancer [8]. Some studies have suggested that blood CTC enumeration may correlate with tumor burden and anticipate tumor progression [9]. Moreover, blood CTCs have been used to characterize genetic and immunophenotypic changes over time, with the ultimate goal of guiding the management of targeted, individualized therapies [10]. However, CTCs are extremely rare in the blood compared to normal (bystander) blood cells, and are found in ratios as low as one cell per one billion; therefore, isolating these cells has been a challenge [11]. The most successful isolation techniques have been immunocytochemical technologies that label CTCs for separation based on unique surface antigens that distinguish them from normal bystander cells.

OncoCEE™ (Cell Enrichment and Extraction) microfluidic platform and CSF CTCs

OncoCEE™ Cell Enrichment and Extraction is a novel technology that has been shown to more efficiently capture and detect CTCs utilizing biotin-tagged antibodies that bind selectively to CTCs. The antibodies are introduced into a suspension of blood cells intending that only CTCs will then display surface biotin molecules. Next, the cell suspension is passed through a microfluidic channel that contains about 9000 transverse, strategically placed streptavidin coated posts. A CTC making contact with a post has the opportunity to engage in a biotin-streptavidin reaction that immobilizes the cell, and creates an enriched sample. Standard marker and FISH analysis of the cells can be completed within the device. Bystander blood cells remain in suspension and pass through the channel. We hypothesize that such methodology can also be used to isolate CTCs in the CSF and diagnose LM in solid tumors with an increased sensitivity over standard cytopathologic analysis.. We are initiating a pilot study to evaluate the potential of this technology in this setting.

**Columbia University Medical Center
Herbert Irving Comprehensive Cancer Center**

4. STUDY DESIGN

4.1 General Design

This study will prospectively enroll 36 evaluable subjects with solid tumors who are undergoing workup for clinical suspicion of leptomeningeal metastasis (LM) for unequivocal or suspicious findings by imaging or clinical determination. Neuroimaging consisting of MRI of the brain or total spine (or both, as clinically indicated) will be obtained in all patients. Patients will also undergo a lumbar puncture and standard CSF evaluation, which may consist of intracranial pressure measurement, CSF protein, glucose, white and red cell analysis, infectious cultures, as well as conventional cytopathologic analysis (cytocentrifuge). An additional CSF sample will be obtained for evaluation of CSF CTCs by OncoCEE™ technology and cell-free DNA (recommended amount: 1 tube, 10 mL) at the time of lumbar puncture.

We will define LM as previously described [14]. Patients will be considered to have a definitive diagnosis of LM if they have a positive CSF cytology.. We will accrue 10 patients with positive cytology. Unequivocal MRI findings will be defined as leptomeningeal enhancement with subarachnoid nodules, enhancement in basal cisterns, or enhancement/clumping of nerve roots. Findings such as multiple superficial brain metastases, intraventricular masses, dural enhancement associated with epidural metastasis, or new hydrocephalus will be considered suspicious but nondiagnostic. Patients with unequivocal or suspicious findings on imaging or clinical findings (without known CSF positivity) will be eligible for this study (n=36).

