6. ADVERSE EVENTS: LIST AND REPORTING REQUIREMENTS

6.1 Adverse events

This protocol does not require any additional tissue sample collection than that which would be standard of care, except for the additional tube of CSF collected during standard collection procedures during routine investigation of LM. Experimental data from this research will not influence the therapeutic decisions. The treating physician will not be informed of the result. The rate of adverse events is expected to be very low.

Risk will primarily be attributed to the additional CSF required for the study; withdrawing excess amounts of CSF can induce nausea, positional headache or light headedness.

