7.5 Case Report Forms

The study case report form (CRF) is the primary data collection instrument for the study. All data requested on the CRF must be recorded. All missing data must be explained. If a space on the CRF is

**Columbia University Medical Center
Herbert Irving Comprehensive Cancer Center**

left blank because the procedure was not done or the question was not asked, write “N/D”. If the item is not applicable to the individual case, write “N/A”.

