8.2 Size/Accrual Rate

Based on an anticipated accrual rate of 1-2 subjects / month, we anticipate a 24 month enrollment period in order to accrue 46 subjects.

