8.3 CSF Analysis (Mandatory)

Patients will undergo a lumbar puncture and standard CSF evaluation, which may consist of intracranial pressure measurement, CSF protein, glucose, white and red cell analysis, infectious cultures, as well as conventional cytopathology analysis (cytocentrifuge). Standard CSF evaluation will be performed at

**Columbia University Medical Center
Herbert Irving Comprehensive Cancer Center**

Columbia University Medical Center. An additional 10 mL CSF sample will be obtained for evaluation of CSF CTCs in a CEE-Sure™ collection tube (Biocept Inc., San Diego, CA); this sample will be delivered to Biocept's laboratory for processing, and it will be evaluated for CTCs using OncoCEE™ microchannel technology. This CSF sample will also be tested for cell-free circulating tumor DNA (ctDNA). Depending on available technology, we may explore Next-Generation DNA sequencing to evaluate the sample for somatic mutations.

OncoCEE™ microchannels are manufactured at Biocept, Inc. (San Diego, CA). The cells will be run through the microchannel, captured using an antibody cocktail, and stained with a mixture of anti-cytokeratin antibodies labeled with AlexaFluor-488. Cells will be simultaneously stained with anti-CD45 labeled with AlexaFluor-594. ER/PR ICC will be performed using anti-ER (Abcam, Cambridge, MA) and anti-PR (Epitomics Inc, Burlingame, CA) monoclonal rabbit antibodies and secondary anti-Rabbit antibody labeled with AlexaFluor-546. The microchannels will undergo microscopic analysis for enumeration of CK+/CD45-/DAPI+ (CTC identification), CK-/CD45+/DAPI+ (background white blood cells), and all CK+ cells will be assessed for ER/ PR/HER2 positivity, if breast cancer. The microchannels will undergo immediate manual microscopic analysis for enumeration of CTCs and assessment of ER/PR followed by taking images and X/Y coordinates recorded using Olympus Bx51 fluorescent microscopes equipped with appropriate filters and the Metasystems imaging system v5.2 (Metasystems GmbH, Germany)[10, 15]. Depending on available technology, we will explore Next-Generation DNA sequencing to evaluate the CSF for somatic mutations. The samples will be stored at Biocept for potential future testing, which may include the assessment of somatic alterations. No germline testing will be performed.

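### Does the undefined term evaluable, with a 10 mL device tube recommended in one section and stated outright in another, leave the primary sensitivity denominator open?

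*Combined protocol and SAP*

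**What the plan says.** Two sections describe the device tube. Section 4.1 presents the volume as a recommendation, "cell-free DNA (recommended amount: 1 tube, 10 mL) at the time of lumbar puncture". Section 8.3, whose heading marks the CSF analysis as mandatory, says "An additional 10 mL CSF sample will be obtained for evaluation of CSF CTCs in a CEE-Sure™ collection tube". Section 8.3 also sends the tube to the manufacturer's laboratory and uses the same sample for tumour DNA testing.

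Section 8.1 gives the sample size: "We will have 80% power to detect this difference on the first lumbar puncture in 36 evaluable patients", for sensitivities of 75% against 50% at a two-sided alpha of 0.05. It expects about 32 of the 36 to have leptomeningeal metastasis (LM), adds 10 evaluable patients with positive CSF, and totals 46. The word evaluable recurs in the synopsis and in Sections 4.1, 5.1 and 5.2, without a definition.

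Elsewhere the same total appears without that word. Section 5.4 says "CSF collection from 46 eligible breast cancer subjects is estimated to take approximately 24 months" and Section 8.2 says "we anticipate a 24 month enrollment period in order to accrue 46 subjects". On missing values, Section 7.5 says "All missing data must be explained" and has staff mark procedures that were not done. Section 5.5.2 lists specimen collection among the data on the case report form.

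**The concern.** A recommended volume allows a smaller one, and the plan gives reasons why a tube might be short or fail. Section 6.1 warns that "withdrawing excess amounts of CSF can induce nausea, positional headache or light headedness", one tube serves two assays, and it is shipped to an outside laboratory. If some tubes give no result, someone must decide whether those patients count.

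A tube with no result detects nothing. Leaving it out gives the device a higher sensitivity than counting it as a miss. If adequacy were judged after the cell count was known, short tubes with tumour cells could be kept and short tubes without them set aside. Either choice would favour the hypothesis under test. With about 32 LM patients, a few tubes could decide significance. The total of 46 also contains no visible allowance for non-evaluable patients.

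**Working it through.** **1. The volume wording.** Section 4.1: 10 mL, recommended. Section 8.3: 10 mL, to be obtained. The amount is the same; one reads as a target and the other as a description of the laboratory procedure. Aligning the words would not settle who enters the sensitivity comparison. No volume is proposed here.

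**2. What 46 counts.** Section 4.1 enrols 36 evaluable subjects, Section 5.1 accrues 10 evaluable patients, and Section 8.1 adds them: 36 + 10 = 46. The plain reading is 46 evaluable. Sections 5.4 and 8.2 repeat the total loosely when discussing timing and do not set up a second analysis set. Accrual at 1 to 2 a month for 24 months gives 24 to 48 patients, so even the top rate leaves 48 − 46 = 2 spare. That bears on duration, which the plan gives as approximate.

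**3. The plan's power figure.** Section 8.1 names neither the test nor the share of discordant pairs, so 80% at 36 cannot be reproduced uniquely. Take the paired McNemar normal approximation with difference d = 0.25 and assumed discordance p = 0.30 (cytology-only 0.025, device-only 0.275):

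n = (1.96√p + 0.8416√(p − d²))² / d² = (1.0735 + 0.4101)² / 0.0625 = 35.2, rounded up to 36, with power 0.809.

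The stated figure is therefore attainable if about 30% of pairs are discordant. That share is an assumption.

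**4. Effect of the two rules.** Let f be the share of tubes with no result, assumed unrelated to either test. The documents give no f; 5% to 20% is illustrative. Sensitivity is 0.75 with failures left out and 0.75(1 − f) with failures counted as not detected. Power uses the step 3 inputs with 36 patients at the start.

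| f | n if left out | Power, left out | Sensitivity if counted | Difference from 50% | Power, counted |
|---|---|---|---|---|---|
| 5% | 34 | 0.785 | 71.3% | 21.3 points | 0.639 |
| 10% | 32 | 0.758 | 67.5% | 17.5 points | 0.457 |
| 20% | 29 | 0.712 | 60.0% | 10.0 points | 0.172 |

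Replacing failures until 36 are evaluable needs 36/(1 − f) = 38, 40 or 45 patients and retains the power of 0.809.

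Exact McNemar power in the 32 expected LM patients, with all 25% discordance favouring the device, is 85% with no failures. Counting failures gives 58% at 5% and 35% at 10%. Leaving them out gives 80% and 77%.

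**5. How few tubes could matter.** Two-sided exact McNemar p-values, device-only against cytology-only positives:

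- 9 v 1: 2(1 + 10)/1024 = 0.0215. One cytology-positive failure counted against the device makes it 9 v 2: 2(1 + 11 + 55)/2048 = 0.0654.
- 8 v 0: 2/256 = 0.0078. One such failure makes it 8 v 1: 2(1 + 9)/512 = 0.039.
- 10 v 1: 2(1 + 11)/2048 = 0.0117. One such failure makes it 10 v 2: 2(1 + 12 + 66)/4096 = 0.039.
- A second such failure takes the last two past 0.05: 8 v 2 gives 2(1 + 10 + 45)/1024 = 0.109, and 10 v 3 gives 2(1 + 13 + 78 + 286)/8192 = 0.092.
- A failure in a cytology-negative patient leaves the discordant counts, and so p, unchanged.

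The loss of significance thus depends on the starting split and on which patients' tubes fail.

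**6. Direction.** Failures can occur on either side. If an unsatisfactory cytology is also counted as not detected and the device is positive, the pair becomes device-only and helps the device. Leaving that patient out works against it.

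**The case for a change.** The strongest case for a change is that the plan states a two-sided alpha, 80% power and a comparative aim, so calling it a pilot does not excuse an unwritten analysis set. *Evaluable* also governs entry: Section 5.2 closes the study to patients with earlier positive CSF once 10 evaluable ones have been accrued. The laboratory that counts the cells belongs to a company listed as a funder, and no section says adequacy is judged without sight of the results. A definition would take one short paragraph.

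The missing definition stands, as does the arithmetic: where failures occur, the choice of rule can matter. Fixing the definition before results are seen, and reporting how many samples failed, is good practice.

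The claim of a built-in bias does not stand. No section describes excluding tubes after counting. Moving from 21/32 (66%) to 21/28 (75%) by setting aside four short tubes is conjecture. Section 6.1 describes symptoms from excess withdrawal and does not predict short draws. Cytology is read at the study centre and cell counting is done elsewhere on de-identified samples; this is not a blinding rule, but it separates the two readings. Specimen data and reasons for missing values are to be recorded, so both analyses could be reported.

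**Conclusion.** No change to the plan follows. The two volume statements name the same 10 mL, and the difference in wording is clerical. The undefined term is a gap that an analyst would fill sensibly: an evaluable patient has both results from the first puncture, a result the laboratory reports is used as reported, and accrual continues to 36 + 10. If failure is unrelated to either test's result, that reading leaves the planned 75% against 50% intact and costs only numbers: power of 0.785 instead of 0.809 at 5% failures without replacement, and nothing with replacement.

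Counting failed tubes as not detected is a legitimate alternative that asks how the device performs in routine use, failures included. At 5% failures it lowers sensitivity by 75 − 71.3 = 3.7 points (3.75 before rounding) and gives exact power of 58%, against 80% with failures left out. Either rule is defensible if fixed before results are seen, so this is a trade-off and not an error.

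These figures rest on an assumed failure rate and assumed discordance, neither of which the documents give. If failures were common and concentrated in samples with few tumour cells, the evaluable-only figure would flatter the device; nothing in the documents shows this. Whether sensitivity is computed on 36 or on the expected 32 patients is a separate question, not settled here.
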